8.1 General Principles

The objective of the data screening is to assess the quantity, quality, and statistical characteristics of the data relative to the requirements of the planned analyses.

8.2 Data Handling and Electronic Transfer of Data

The Amgen Global Study Operations-Data Management (GSO-DM) department will provide all data to be used in the planned analyses. This study will use the [RAVE](#) database.

All data collected in the eCRF will be extracted from RAVE. Protocol deviations will be transferred from eClinical. Final PK data for all randomized subjects will be transferred

from statistical programming to Amgen's CPMS group. Unblinded subject and box ID randomization lists will be provided by Amgen's randomization group and the IVRS when the study stops. Details on data transfer will be provided in the Data Transfer Plan.

8.3 Handling of Missing and Incomplete Data

8.3.1 Patterns of Missing Data

Subjects may be missing specific data points for various reasons. In general, data may be missing due to a subject's early withdrawal from study, a missed visit, or non-evaluability of a data point or an endpoint at a particular point in time. In the Data Issue Identification and Resolution (DIIR) processes, queries will be made to the sites to distinguish true missing values from other unknown values (eg, due to measurement of sample processing error).

All attempts will be made to capture missing or partial data for this trial prior to the data lock. The frequency and pattern of missing data for efficacy endpoints will be assessed through descriptive summaries of the measurements over time.

8.3.2 Handling of Incomplete Dates

Adverse event and concomitant medication with completely or partially missing start **and** stop dates will be queried.

After the issue is queried, if the date is still incomplete with year only or year and month only, the start **or** stop date will be imputed as described in Table 1 below.

Table 1. Imputation Rules for Incomplete Dates

	Missing	Imputation	Exception
Start date (AE and concomitant medication)	Day	1	Default to Study Day 1 if an event starts the same year and month as Study Day 1
	Day/Month	1-Jan	Default to Study Day 1 if an event started the same year as Day 1
End date (AE and concomitant medication)	Day	Last day of the month	
	Day/Month	31-Dec	

If the stop date is entirely missing, assume the event or medication is ongoing.

8.4 Detection of Bias

This study has been designed to minimize potential bias by the use of randomization of subjects into treatment groups and the use of blinding. It is not expected that any study conduct procedures or statistical analyses will introduce bias in the study results or conclusions. However, potential sources of bias in this study include:

- Major protocol deviations likely to impact the analysis and interpretation of the efficacy endpoints
- Subject level unblinding before final database lock and formal unblinding

Important protocol deviations likely to impact the analysis and interpretation of the efficacy endpoints will be tabulated in the Clinical Study Report (CSR).

Any unblinding of individual subjects prior to formal unblinding of the study will be documented in the CSR. The impact of such unblinding on the results observed will be assessed.

8.5 Outliers

Various methods, including univariate summaries, histograms, scatter plots, box plots, and line graphs, may be used to identify outliers in key safety and efficacy variables. Extreme data points will be identified during the blinded review of the data prior to database lock. Such data points will be reviewed with clinical data management to ensure accuracy. The primary analyses will include outliers in the data. Sensitivity analyses may be undertaken if extreme outliers for a variable are observed.

8.6 Distributional Characteristics

Distributional assumptions for the planned analyses of the primary and secondary endpoints will be assessed. If the assumptions are not met, then alternative methods will be utilized. The use of alternative methods will be fully justified in the CSR.

8.7 Validation of Statistical Analyses

Programs will be developed and maintained, and output will be verified in accordance with current risk-based quality control procedures.

Tables, figures, and listings will be produced with validated standard macro programs where standard macros can produce the specified outputs.

The production environment for statistical analyses consists of Amgen-supported versions of statistical analysis software; for example, the SAS System version 9.4 or later.

9. Statistical Methods of Analysis

9.1 General Considerations

Unless specified otherwise, efficacy analyses will be performed on the FAS by randomized treatment group, and safety analyses will be performed on the FAS by actual treatment group.

For the Primary Analysis (as described in Section 7.2), all data up to the primary analysis data cut-off date will be included. Based on the snapshot for the primary analysis, efficacy and safety analyses will be performed. Testing will be performed for endpoints defined up to week 36. Descriptive summary will be provided for all available visits by period (ie. Treatment period and extended safety follow-up period).

For the End of Treatment Period Analysis (as described in Section 7.3), all data up to the end of treatment period analysis cut-off date will be included. Testing will be performed for endpoints defined up to week 48. Descriptive summary will be provided for all available visits by period (ie. Treatment period and extended safety follow-up period).

For the Final analysis (as described in Section 7.4), all efficacy and safety analyses during the extended follow-up period will be performed based on the snapshot for the final analysis.

Subject disposition, demographics, baseline characteristics, and exposure to IP will be summarized.

All categorical variables will be summarized using the number and percent of subjects and all continuous variables will be summarized using mean, standard error or standard deviation, median, minimum, maximum, and number of subjects with observations.

Multiplicity Adjustment Method:

The Hochberg procedure will be used to control the type I error for multiple comparisons between active and placebo groups in the primary endpoint. The primary endpoint includes percent change in Lp(a) from baseline at week 36 for olpasiran SC Q12W groups and placebo. Percent change in Lp(a) from baseline for Q24W group is defined as exploratory endpoint.

A summary of the analyses for each planned analysis can be found in Table 2.

Table 2. Summary of Analyses

Analyses	Primary Analysis (all data up to primary analysis data cut-off date)	End of Treatment Period Analysis (all data up to End of Treatment Period Analysis data cut-off date)	Final Analysis (all data based on final snapshot)
Efficacy	
 • Repeated measures model for primary endpoint, secondary endpoints defined at week 36, and exploratory endpoints of percent change from baseline in Lp(a), LDL-C and ApoB up to week 36. • Multiplicity adjustment for primary endpoint, as described above in Multiplicity Adjustment Method • Sensitivity analysis for primary endpoint using non-parametric (Quade test) approach based on CAS • Cochran-Mantel Haenszel (CMH) test adjusted by the stratification factors will be used for exploratory endpoints of Lp(a) achievements 	
 • Repeated measures model for primary endpoint, secondary endpoints defined at week 36 and week 48 and exploratory endpoints of percent change from baseline in Lp(a), LDL-C and ApoB up to week 48. Testing is performed up to week 48. • Multiplicity adjustment for primary endpoint, as described above in Multiplicity Adjustment Method • Sensitivity analysis for primary endpoint using non-parametric (Quade test) approach based on CAS • Cochran-Mantel Haenszel (CMH) test adjusted by the stratification factors will 	
 • Descriptive summary for efficacy endpoints in the extended follow-up period

	
(including achievement of Lp(a) < 125nmol/L) up to week 36
 
 • Descriptive summary for all efficacy endpoints by period (ie. Treatment period and extended safety follow-up period) 	
be used for exploratory endpoints of Lp(a) achievements (including achievement of Lp(a) < 125nmol/L) up to week 48
 
 • Descriptive summary for all efficacy endpoints by period (ie. Treatment period and extended safety follow-up period) 	
Safety	
 • Summary by actual treatment group by period (ie. Treatment period and extended safety follow-up period) 	
 • Summary by actual treatment group by period (ie. Treatment period and extended safety follow-up period) 	
 • Summary by actual treatment group in the extended follow-up period

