The detection and documentation procedures for adverse device effects described in this protocol apply to all Non-Amgen medical devices provided for use in the study (see Section 6.1.2 for the list of Non-Amgen medical devices).

Adverse Device Effect Definition

An adverse device effect is any adverse event related to the use of a combination product or medical device. Adverse device effects include, but are not limited to, adverse events resulting from insufficient or inadequate instructions for use, adverse events resulting from any malfunction of the device, or adverse events resulting from use error or from intentional misuse of the device.

Recording Adverse Events and Serious Adverse Events

Adverse Event and Serious Adverse Event Recording

- When an adverse event or serious adverse event occurs, it is the responsibility of the investigator to review all documentation (eg, hospital progress notes, laboratory, and diagnostics reports) related to the event.
- The investigator will then record all relevant adverse event/serious adverse event information in the Event case report form (CRF).
- The investigator must assign the following adverse event attributes:
 - Adverse event diagnosis or syndrome(s), if known (if not known, signs or symptoms);
 - Dates of onset and resolution (if resolved);
 - Did the event start prior to first dose of investigational product, other protocol-required therapies;
 - Assessment of seriousness;
 - Severity (or toxicity defined below);
 - Assessment of relatedness to investigational product (**olpasiran/placebo**) **and/or other protocol-required therapies**;
 - Action taken, and
 - Outcome of event.
- If the severity of an adverse event changes from the date of onset to the date of resolution, record as a single event with the worst severity on the Events CRF.
- It is not acceptable for the investigator to send photocopies of the subject's medical records to Amgen in lieu of completion of the Events CRF page.
- If specifically requested, the investigator may need to provide additional follow-up information, such as discharge summaries, medical records, or extracts from the medical records. In this case, all subject identifiers, with the exception of the subject number, will be blinded on the copies of the medical records before submission to Amgen.

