5.3 Other Study Related Definitions

Analytical Study Week Assignments

Analytical windows will be used to assign parameter measurements to study weeks. The algorithm is provided in [Appendix A](#).

Actual Treatment Group

A subject's actual treatment group is the randomized treatment group, unless the subject receives treatment throughout the study that is different than the randomized treatment group assignment, in which case the actual treatment group is the treatment received.

Investigational Product (IP)

Olpasiran SC 10 mg Q12W, 75 mg Q12W, 225 mg Q12W, 225 mg Q24W and placebo SC Q12W.

Study Exposure Period in Months

For each randomized subject, Study Exposure Period = (EOS date – Randomization Date + 1) / 365.25 * 12

IP Exposure Period in Months

IP Exposure Period = [min (Last IP Dose Date + 84 days, EOS Date) – First IP Dose Date + 1] / 365.25 * 12

Treatment Emergent Adverse Event in Treatment Period

Events categorized as Adverse Events (AEs) starting on or after first dose of investigational product as determined by “Did event start before first dose of investigational product” equal to No or missing on the Events eCRF and up to the End of Treatment Period date, or EOS date for subjects who early discontinue the study during the treatment period.

Treatment Emergent Adverse Event in Extended Safety Follow-up Period

Events categorized as Adverse Events (AEs) starting on or after first dose of investigational product (as determined by “Did event start before first dose of

investigational product” equal to No or missing on the Events eCRF) and on or after the Extended Safety Follow-up Period Start Date, and up to the EOS date.

Reflexive Approach for LDL-C and VLDL-C

Reflexive approach for LDL-C and VLDL-C is only applicable for the central lab data. For all analyses related to LDL-C and VLDL-C, unless specified otherwise, the following reflexive approach will be used.

When calculated LDL-C is less than 40 mg/dL or triglycerides are > 400 mg/dL, the ultracentrifugation (UC) LDL-C value from the same blood sample will be used instead of calculated LDL-C and the UC VLDL-C value from the same blood sample will be used instead of calculated VLDL-C, if available.

6. Analysis Sets

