7.4 Final Analysis

Final analysis will be performed when all randomized subjects either complete the extended safety follow-up and ended the study or early terminate from the study. At that time, the database related to the final analysis will be cleaned, processed and the database will be locked. All efficacy and safety analyses during the extended follow-up period will be performed.

8. Data Screening and Acceptance

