9.5.3 Analyses of Exploratory Efficacy Endpoint(s)

Exploratory endpoints of percent change from baseline at scheduled visits in Lp(a), LDL-C and ApoB will be analyzed using repeated measures linear effects model including terms for treatment group, stratification factors, scheduled visit and the interaction of treatment group with scheduled visit will be used; and achievements of Lp(a) at scheduled visits (including achievement of Lp(a) < 125nmol/L) will be analyzed using CMH test as specified in Table 2. Subject incidence of positively adjudicated events (overall and by event type as defined in protocol) and change from baseline in PROMIS Global Health measures at scheduled visits will be summarized by treatment group using descriptive statistics.

Descriptive summary for non-HDL-C, HDL-C, VLDL-C and Triglycerides will be provided by scheduled visits.

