9.6.2 Laboratory Test Results

Selected laboratory parameters will be summarized using descriptive statistics at scheduled visits. Laboratory shift tables using the CTCAE v5.0 or later grading will be used for analytes of interest, when applicable. The results will be based on the maximum (e.g., worst) shift from baseline to the EOS.

In addition, creatine kinase (CK) and liver function test (LFT) abnormalities will be assessed by the incidence overall and by visits of the following categories:

- CK > 5 x ULN
- CK > 10 x ULN
- ALT or AST > 3 x ULN
- ALT or AST > 5 x ULN

- Total bilirubin > 2 x ULN
- (ALT or AST > 3 x ULN) and Total bilirubin > 2 x ULN and Alkaline Phosphatase <2 x ULN

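### No listed analysis updates the treatment-period safety tables after the end-of-treatment cut-off, so late reports and late changes of status can go uncounted

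*SAP*

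**What the plan says.** **Scope of the final analysis.** SAP 7.4 states: "All efficacy and safety analyses during the extended follow-up period will be performed". Protocol 9.4.1.4 says the same. SAP 9.1 repeats it: "all efficacy and safety analyses during the extended follow-up period will be performed based on the snapshot for the final analysis". In the safety row of Table 2, the primary and EOT columns name both periods, whereas the final column reads "Summary by actual treatment group in the extended follow-up period".

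**Period rule.** Under SAP 5.3, a TEAE belongs to the follow-up set if it starts "on or after the Extended Safety Follow-up Period Start Date, and up to the EOS date". SAP 5.1 places that start date one day after the End of Treatment Period Date. Earlier onsets fall in the treatment-period set. The SAP defines no third set running from first dose to end of study (EOS).

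**Recording rule.** When severity changes over the course of an event, protocol Appendix 4 tells the investigator to "record as a single event with the worst severity on the Events CRF". The completion instructions for the contingency serious-event form ask for the date the event first began, even if it met a serious criterion only later.

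**Adjudicated events.** SAP 9.5.3 plans "Subject incidence of positively adjudicated events" by treatment group and gives no period rule.

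**Text pointing to a wider scope.** SAP 9.6.2 bases laboratory shifts on the "maximum (e.g., worst) shift from baseline to the EOS". SAP 9.6.1 says adverse-event summaries take in every treatment-emergent event on the event form, including events reviewed by the clinical events committee. The Table 2 header for the final column refers to all the data in the final snapshot.

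**The concern.** Adverse events are collected to EOS (protocol 8.2.4.1) and followed to resolution or stabilization (protocol 8.2.4.3). Treatment-period records can therefore be added or changed after the EOT snapshot. If the final tables select on onset date and the treatment-period tables are frozen at the EOT cut-off, such changes reach neither.

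At stake is the completeness of the serious, fatal and adjudicated cardiovascular counts in the final report. In arms of about 58 subjects, a single such case is visible. Timing also matters: protocol 9.4.1.3 unblinds the sponsor after the EOT snapshot. A decision after that point to rebuild or merge safety tables would be taken with treatment assignment known, so it is better fixed in the SAP beforehand.

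**Working it through.** **1. The plan's own safety figure.** SAP 3.2 gives 192 subjects in the active arms, 5% drop-out, and 95% confidence of seeing at least one case at an incidence of 1/60.
- Evaluable: 192 × 0.95 = 182.
- 1 − (1 − 1/60)^182 = 95.3%. The figure reproduces.

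The point does not depend on this figure; it rests on comparing the period rule with the scope of each analysis.

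**2. Safety tables listed at each analysis (SAP Table 2).**

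| Analysis | Treatment-period tables | Follow-up tables |
|---|---|---|
| Primary | yes, to its cut-off | yes, to its cut-off |
| EOT | yes, to its cut-off | yes, to its cut-off |
| Final | none listed | yes |

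**3. Time in which records can still change.** SAP Appendix A puts week 48 at day 337 and week 72 at day 505. The difference is 505 − 337 = 168 days, or 24 weeks. For a subject who reaches week 48 just before the EOT cut-off, nearly all of this falls after it. For early enrollees, part of it falls before.

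**4. Three kinds of treatment-period event, traced through the rules.**

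| Event (onset in the treatment period) | EOT tables | Final tables as scoped | What is lost |
|---|---|---|---|
| First reported after the EOT cut-off | absent, not yet known | absent, onset too early | the whole event |
| Reported before the cut-off, serious or fatal later | in the all-TEAE table | absent, onset too early | its count as serious or fatal |
| Reported before the cut-off, positively adjudicated later | in the all-TEAE table | undetermined, no period rule | possibly its adjudicated count |

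The third row is undetermined because SAP 2.1 makes adjudicated events an exploratory endpoint and the final efficacy column of Table 2 covers the follow-up period. Nothing says whether the date of the event or the date of adjudication decides the period.

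**5. No combined set.** Subject incidences by period do not add. With p1 in treatment and p2 in follow-up, on the same denominator, whole-study incidence lies between max(p1, p2) and p1 + p2. For illustration, 4% and 3% are compatible with anything from 4% to 7%.

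**6. Size, as illustration only.** The documents give no share q of cases reported late. Detection at 1/60 becomes 1 − (1 − (1 − q)/60)^182:

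| q (assumed) | Detection, 182 subjects |
|---|---|
| 0 | 95.3% |
| 1% | 95.2% |
| 2% | 95.0% |
| 5% | 94.5% |
| 10% | 93.6% |

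At the enrolled size (4 × 58 = 232 active subjects; 232 × 0.95 = 220), detection is 97.5% at q = 0 and 96.4% at q = 10%. The effect on detecting an event type is slight. What matters is the accuracy of small counts.

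**The case against.** The best counter-argument is that the plan is loosely worded and does not exclude anything. The Table 2 header covers all data in the final snapshot, SAP 9.6.1 puts no period limit on adverse-event summaries, and shifts that run to EOS can be completed only with final data. That the passages are unreconciled stands. They do not amount to a commitment to re-run, however. The header names the data source, and SAP 9.1 ties that same snapshot to the follow-up period. SAP 9.6.1 relies on a term that SAP 5.3 defines only period by period.

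Second, the EOT analysis waits until every subject has had the opportunity to complete week 48, and the data are cleaned first. Protocol 9.4.1.3 even speaks of a locked database before unblinding at that point. This stands as a limit on size: exposure is mainly through later enrollees and late updates. The plan expects about 120 subjects to have had the opportunity to complete week 36 when about 240 have had it for week 24. Those 120 are at least 12 weeks ahead of the last subject. If they stay on study, at least 120 × 12/52 = 28 of the planned minimum 290 × 24/52 = 134 subject-years of follow-up precede the EOT cut-off, about 21%.

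Third, there are safeguards. Serious events are reported within 24 hours, an unblinded data review team sees accumulating safety data, death by any cause is an adjudicated event, and study discontinuation is tabulated by reason. These protect subjects and make a wholly unreported death unlikely. They do not correct the adverse-event tables.

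Fourth, week 48 is not an arbitrary boundary. It falls 12 weeks after the last dose at week 36, matching the 84-day window in the SAP 5.3 exposure definition. That stands, and the point does not rely on the boundary being wrong.

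**Conclusion.** The point holds as a gap in what the final analysis is committed to produce. Followed as written, the period rule and the final scope leave late-reported treatment-period events out of every listed table. They also leave later serious or fatal status out of the corresponding counts, and late adjudication without a defined place.

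Two stronger readings are not supported. A reader might infer that all treatment-period events that turn serious or fatal, or are adjudicated late, vanish from the report. They do not: if reported before the EOT cut-off, they remain in the EOT all-TEAE table. A reader might also want to estimate missing deaths by applying a mortality rate to the follow-up time. The documents give neither a mortality rate nor the share of deaths arising from earlier events, and some of the follow-up precedes the cut-off.

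The conclusion assumes that the electronic event form keeps the first onset date, as the contingency form does; the electronic form's own completion rules are not in the documents. The number of events is probably small and cannot be estimated. Safety is summarized descriptively and the primary endpoint is untouched, so the severity is should-fix.

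**What to change.** In SAP 7.4, SAP 9.1 and the final column of Table 2:

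- State that the treatment-period tables of adverse events, serious events, fatal events, laboratory shifts and adjudicated events will be regenerated from the final locked database, using seriousness, outcome and adjudication status as at final lock.
- Add to SAP 5.3 a TEAE set from first dose to EOS, and summarize it counting each subject once per term.
- State in SAP 9.5.3 which date assigns an adjudicated event to a period.
- Align SAP 9.6.1, SAP 9.6.2 and the Table 2 header with this scope, and preferably list the treatment-period records changed since the EOT snapshot.

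Protocol 9.4.1.4 carries the same restriction. SAP section 10 could record the wider scope as an addition to it.

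The cost is SAP wording and a re-run of existing programs, with no new data. The downside is that treatment-period counts in the final report may differ slightly from those in the EOT report; the list of changed records would explain the differences.
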